to insulin resistance. The sum of all sarcolemmal disaturated 1,2-DAG species were significantly greater in T2D compared to lean volunteers (Figure 2A), and was inversely related to insulin sensitivity (Figure 2B). Notably, 1,3-disaturated DAG content was not different between groups revealing isomer specificity. We previously showed that membrane di-saturated DAG content predicted PKC activation and insulin resistance (26). These data agree and suggest that sarcolemmal DAG containing saturated acyl side chains represent membrane accumulation of DAG that is particularly negative for insulin sensitivity.

PKC ϵ activity is increased in obesity and T2D. We

measured the membrane/cytosol ratio of PKC ϵ , which is commonly used as a surrogate for PKC activity. We found significantly greater PKC ϵ activation in obese and T2D subjects compared to lean controls (Figure 3), with no significant differences found for PKC β II, δ , and θ isoforms. These data are consistent with greater PKC activation from sarcolemmal DAG accumulation.

Sarcolemmal C18:0 ceramide accumulates in insulin resistance. Of the 9 sarcolemmal ceramide species measured, only C18:0 ceramide was significantly greater in T2D compared to lean (Figure 4A), and was inversely related to the rate of glucose disappearance during an insulin clamp (Figure 4B). In a pilot study sarcolemmal C18:0 ceramide decreased by 21% after a combined weight loss

and exercise training intervention. These data parallel a recent publication by our lab showing C18:0 muscle ceramides significantly related to insulin resistance in a different cohort (27). C18:0 ceramide antagonizes an inhibitor of PP2A, resulting in increased PP2A activity (28). Combined, these data suggest that sarcolemmal C18:0 ceramide may promote insulin resistance, and due to the location may explain the canonical pathways of ceramide induced insulin resistance, including activation of PP2A activity, and inhibition of AKT phosphorylation in response to insulin.

Mitochondrial/ER ceramide accumulates in insulin

resistance. Mitochondrial ceramide content was greater in T2D compared to lean individuals, which is largely explained by C22:0 and C24:0 species (Figure 7A). Total ceramide content was inversely related to

insulin sensitivity (Figure 7B). These data are consistent with the hypothesis that mitochondrial ceramides promote insulin resistance.

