stress. Basal acyl-carnitines revealed accumulation of many long chain acyl-CoA's in type 2 diabetics including C18:0, C18:2-OH, and C20:4, which are thought to promote insulin resistance (Figure 11A). A significantly decreased GSH/GSSG ratio in type 2 diabetes individuals compared to lean volunteers suggest a more oxidized state, consistent with increased oxidative stress in insulin resistance (Figure 11B).

DAG and ceramide decrease mitochondrial

function. We administered 1,2-DAG, ceramide, dihydroceramide, and vehicle controls to isolated rat mitochondria in vitro to evaluate the impact on mitochondrial respiration using pyruvate and malate as substrates. DAG and ceramide decreased state 3 respiration, with no changes observed with dihydroceramide administration (Figure 12A and B). State 4 respiration did not change for 1,2-DAG and dihydroceramide, but increased significantly with increasing doses of ceramide. Both 1.2-DAG and ceramide decreased ADP/O ratios (Figure 13A and B), while dihydroceramide had no effect. These data indicate 1.2-DAG and ceramide reduced mitochondrial respiration and coupling, and are consistent with accumulation of mitochondrial lipids altering mitochondrial function.

Protocol Template CF-146, Effective 7/10/11

IV. Research Methods

A. Outcome Measure(s):

Primary outcomes:

Aim 1: Change in insulin sensitivity, change in sarcolemmal Di-C18:0 DAG and C18:0 ceramide, change in PKCepsilon and PP2A activity

Aim 2: Change in insulin sensitivity, change in mitochondrial/ER total DAG and ceramide content, change in state 3 mitochondrial respiration, change in GSH/GSSG, change in C18:0, C18:2-OH, and C20:4 acylcarnitines, change in GRP78

Aim 3: Change in mitochondrial state 3 and state 4 respiration in response to DAG and ceramide before and after lifestyle interventions

Secondary outcomes: Changes in other localized lipids and intracellular responses will be exploratory in nature. In addition, we will collect subjective and objective information about sleep and an exploratory analysis.

B. Description of Population to be Enrolled:

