Muscle biopsy – Subcellular fractionation will be performed as described in Figure 1. Diacylglycerol (1,2- and 1,3- isomers), sphingolipids (dihydroceramide, ceramide, glucosylceramide, lactosylceramide, sphingosine, sphingosine-1-phosphate, sphingomyelin), triacylglycerol, phosphatidic acid, and long chain acyl-CoA species will be analyzed by [name] using the lipidomics platform in our laboratory. Subcellular fractions are fortified with internal standards (ISs), lipid extracted, and analyzed by an Agilent 1100 HPLC connected to an API 2000 triple quadrupole mass spectrometer (40). The 1,3- and 1,2- DAG isomers are separated chromatographically using a Hilic 2.1 micron, 3x100mm column. Concentration is determined by comparing ratios of unknowns to odd chain or deuterated internal standards. Incorporation of [U-¹³C]glucose into DAG glycerol, and [U-¹³C] palmitate into the sphingolipid backbone will be used to estimate *de novo* synthesis of DAG and sphingolipids (41; 42). Western blot analysis will quantify PKC translocation of θ , ε , β II, and δ isoforms in basal biopsies, as well as insulin signaling in basal and insulin stimulated biopsies including AKT^{ser473} /total, IRS-1^{Tyr612}/total, and AS160^{Thr642}/total using standard techniques (43). AKT^{Thr34} phosphorylation will be used to estimate PKC ζ activation by ceramide. PP2A activity will be measured using manufacturer instructions (Ser/Thr Phosphatase Assay Kit 1, Billerica, MA).

After the baseline clamp, subjects will be randomized into one of three interventions for three months:

1. Endurance exercise training - Participants will undergo supervised endurance exercise training administered by the Nutrition Obesity Research Center (NORC) Energy Balance Core (see attached letter of support from [name]) using well-established methods (44-48). Participants will perform supervised exercise 4x/week as well as exercise 1x/week on their own. Each 60 min session will include a short warm-up, 40 to 50 min of endurance exercise, and a cool-down. The exercise program will consist primarily of brisk walking or jogging, and will be supplemented with rowing, stepping, or elliptical exercise. The initial exercise prescription will be 30 minutes at 65% of maximal HR. During the first 2 weeks of training, exercise duration and intensity will be gradually increased

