to 45 min at 80 to 85% of maximal HR. This exercise training program resulted in a 9% increase in VO₂max in our pilot study (Figure 6A). Participants will be weighed weekly, and will be instructed to consume more food to prevent weight loss during this intervention. Maximal exercise testing will be performed half way through the intervention, and exercise prescriptions updated every 2 weeks.

2. Diet-Induced Weight loss - The weight loss program will be administered by the Clinical Core of the NORC (see attached letter of support from [name]). Participants will receive a low calorie diet consisting of 4-5 servings of vegetables per day and 4-5 meal replacements (Health Nutrition Technology Inc., Carmel California). No other food intake will be allowed. To reduce the risk of gallstone formation subjects will consume 2 teaspoons (10g) per day of vegetable oil. This diet will provide 890 kcal/d, 75 g of protein, 15 g fat and 110 g of carbohydrate and 100% of the DRI of all vitamins, minerals and micronutrients. This meal replacement program was used in our pilot study with an average 9% weight loss and 62% increase in insulin sensitivity in in 12 weeks (Figures 6B and 6C). Subjects will be weighed

weekly and will meet bi-weekly in group sessions to receive nutritional/behavioral counseling. After the 3month intervention, subjects will transition to their normal diet for 2 weeks of weight maintenance, supervised by research dieticians with extensive experience helping subjects maintain a weight-reduced state.

3. Delayed intervention control – This group of individuals will serve as our free-living control group, and ensure none of the changes observed in the diet-induced weight loss or exercise training interventions are due to receipt of health information, exercise testing, or contact with investigators. After finishing the study, they can choose to undergo the weight loss, exercise training, or combination intervention.

After finishing the intervention, participants will repeat the maximal exercise testing, MRI scan, DEXA measurement of body composition, sleep recording and the insulin clamp study after 2 weeks of weight stability on their typical diet.

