basal respiration rates will vary based on training status and quality of muscle fibers from the biopsy. Permeabilization will be carried out directly in an oxygraph chamber with saponin (20 µg/mL) for 5 min before starting the measurements as previously described (49). To evaluate the in vivo condition, mitochondrial respiration in permeabilized muscle will be determined with glutamate + malate (GM), octanovl carnitine + malate(OM), and succinate as respiratory substrates (Table 2A). In the presence of either GM or OM, respiration is initiated with a saturating concentration of ADP (2 mM) and the Vmax of maximal ADP-stimulated respiration rate or state 3 respiration rate is determined. To evaluate the influence of DAG and sphingolipids on mitochondrial respiration, sphingolipids in isopropyl alcohol (1ul in 2ml respiration buffer), DAG in ethanol (1ul in 2ml respiration buffer), or vehicle controls are then added serially to measure affects of low, medium, and high lipid content. The intactness of mitochondrial membranes will then be validated by cytochrome c tests for each experiment. Only samples passing this quality test will be used further. Oligomycin is then given to measure mitochondrial proton leak. FCCP will then be titrated to uncouple the mitochondria and a maximal rate of the electron transport system rate determined. Antimycin A $(10 \ \mu M)$ is then added to determine the rate of residual oxygen consumption (Rox). Respiration rates are then corrected for Rox. Respiration kinetics of GM and OM will also be determined by adding ADP

Table 2B. Treatments for permeabilized fibers No treatment Vehicle control Lipid control -Triolein Low (1 ug/ml) Medium (2 ug/ml) High (4 ug/ml) Ceramide Low (1 ug/ml) Medium (2 ug/ml) High (3 ug/ml) 1,2-DAG Low (1 ug/ml) Medium (2 ug/ml) High (4 ug/ml) 1,3-DAG Low (1 ug/ml) Medium (2 ug/ml) High (4 ug/ml) Dihydroceramide Low (0.1 ug/ml) Medium (0.2ug/ml) High (0.3 ug/ml)

cumulatively and the maximum rates of respiration (Vmax) and values for apparent KmADP determined using Michelis-Menton kinetics.

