to exercise or weight loss only interventions. If we find minimal changes in insulin sensitivity with either intervention used in isolation, we will move to a combined intervention. Different degrees of success with the interventions are important to provide a spread in the data for changes in localized lipids and insulin sensitivity. An alternative approach would be to provide food for subjects to consume prior to both insulin clamps. We excluded this design because of the possibility of changing muscle lipid species and localization with changing dietary patterns. If individuals cannot maintain their weight within 2kg of starting weight in the exercise only intervention, they will be removed from the study. Our focus in this proposal is on DAG and sphingolipids, however, we will also measure changes in triglyceride, long chain acyl-CoA, and phosphatidic acid to determine other lipids related to changes in insulin sensitivity and/or cellular signaling. If there are no changes in PKC, we will evaluate changes in non-PKC DAG targets such as PKD and RasGRP1/4 to determine if these less studied DAG targets relate to insulin resistance.

Our typical muscle biopsy yield after removal of extra-muscular lipid, is approximately 160mg wet weight, and the tissue required for the assays in this project is 135mg wet weight, allowing all assays to be performed on the majority of biopsies. If muscle yield is limiting, we will prioritize analysis in the following order: subcellular fractionation (50mg) >western blot (15mg) >mitochondrial respiration (25mg) >PP2A activity (10mg) >PKC activity (35mg). We will also evaluate changes in other mitochondrial/ER lipids related to changes in mitochondrial function. In addition to those lipids listed under aim 1, we will also measure cardiolipin content as well as composition.

F. Data Analysis Plan:

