Aim 1: Our statistical methods are rigorous with an a priori statistical analysis plan to test our hypothesis in an unbiased manner, and power analysis based on our own preliminary data. Prior to analysis, data will be analyzed for normality, and any non-normally distributed variables will be log-transformed for use in analytic models. Correlations between the change in sarcolemmal DAG and sphingolipid species and the change in insulin sensitivity will be performed using Pearson's correlation coefficients in the entire study group (n=51). Then, data comparing changes in sarcolemmal DAG and sphingolipid species to changes in insulin sensitivity before and after the intervention will be analyzed using a one-way Analysis of Variance (ANOVA) to examine overall differences between the intervention groups, and using Tukey's procedure to make pair-wise comparisons (e.g control vs. exercise, control vs. diet only) while adjusting for multiple comparisons. Changes in individual DAG and ceramide species will be examined using the Benjamini Hochberg procedure to limit false discoveries (62), and then Principal Component Analysis (PCA) will be used to examine groups of DAG and ceramide species (13). Analyses will be conducted using SAS statistical software ver. 9.4 (Cary, NC). The power analysis is based on changes in sarcolemmal lipids assuming there will be no significant changes in the control intervention. With an overall n of 51, we will have 92% power to detect a Pearson correlation coefficient similar to our preliminary data (Figure 2B, r= -0.45), and 80% power to detect a correlation coefficient as small as -0.38. Pilot data showed sarcolemmal C18:0 ceramide decreased 0.041 ng/ug protein with a SD of .02 after the combined intervention. With an n of 17/group we will have 84.6% power to measure a similar change in sarcolemmal DAG and sphingolipids for individual group comparisons using the Tukey procedure. The type 1 error rate (alpha) will be set at 5% for all comparisons.

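### Nothing withholds allocation from laboratory staff, which leaves blot-read PKC epsilon and the respiration acceptance step open to biased handling after the intervention

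*Combined protocol and SAP*

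**What the plan says.** Section IV.C sets the order of events: "After the baseline clamp, subjects will be randomized into one of three interventions for three months". The active arms are supervised endurance exercise and an 890 kcal/d meal-replacement diet. Of the third arm the protocol says: "This group of individuals will serve as our free-living control group".

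Section IV.A lists the Aim 1 primary outcomes as "Change in insulin sensitivity, change in sarcolemmal Di-C18:0 DAG and C18:0 ceramide, change in PKCepsilon and PP2A activity". State 3 respiration is primary for Aim 2, and state 3 and state 4 respiration are primary for Aim 3.

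On measurement:
- **PKC.** The Muscle biopsy paragraph of IV.C says "Western blot analysis will quantify PKC translocation of" four isoforms, including epsilon. Section III describes the membrane-to-cytosol ratio of PKC epsilon as a measure "which is commonly used as a surrogate for PKC activity". The tissue-priority list in IV.E, however, budgets PKC activity (35 mg) separately from western blot (15 mg).
- **Respiration.** The Mitochondrial Respiration paragraph describes a cytochrome c test of membrane intactness in each experiment, then states: "Only samples passing this quality test will be used further". It gives no numeric cut-off.
- **Lipids and PP2A.** Lipids are measured on the team's own LC/MS platform, as ratios to internal standards. PP2A is measured with a commercial kit.

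On bias control, section IV.F claims an "a priori statistical analysis plan to test our hypothesis in an unbiased manner". Section IV.D refers to de-identified information under confidentiality. No section mentions blinding, masking or coded samples.

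**The concern.** When participants and those delivering the intervention must know the arm, protection has to come from how outcomes are measured. The team holds directional hypotheses: Aim 1 expects less PKC and PP2A activation after the interventions, and Aim 3 expects a weaker response to DAG after exercise training in particular. The power calculations assume no significant change in the control arm. Someone who knows the arm therefore has a different expectation for each arm, and randomisation does not remove an error that enters after allocation. At stake are the comparisons between arms for those primary outcomes in which a person reads a result or decides whether to keep it.

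**Working it through.** The plan states no figure on this point, so the check is mainly a reading of the text.

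**1. Do the nearest safeguards cover the gap?**
- De-identified storage (IV.D) protects privacy. It is not said to hide arm or visit from assay staff.
- The a priori analysis plan (IV.F, Aims 1 and 2) governs what is done with values once they exist, not how a blot is read or a sample accepted.
- Internal standards (IV.C) correct the lipid assay only.
- Randomisation after the baseline clamp means the arm does not yet exist when baseline fresh tissue is processed. It gives no protection to post-intervention tissue, or to stored baseline tissue assayed later.

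**2. Which primary outcomes are exposed?**
- PKC epsilon is exposed if the blot is the readout. Sections III and IV.C point that way; the list in IV.E leaves it unsettled.
- State 3 and state 4 respiration are exposed at the keep-or-drop step. As the sequence is written, the cytochrome c test follows the state 3 measurement and the lipid additions, so the rates have already been observed when the sample is accepted or rejected.
- LC/MS lipids and PP2A leave less to the operator. The text does not describe the GRP78 assay, so it cannot be classed.

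**3. Arm knowledge versus visit knowledge.** Write the observed mean change in arm k as

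observed change(k) = true change(k) + v + a(k),

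where v is error from knowing only that a sample is pre or post, and a(k) is error from knowing the arm. The difference between an active arm j and control c is

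[true(j) − true(c)] + [a(j) − a(c)].

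The term v drops out if it is additive and equal across arms. Only a(j) − a(c) biases the comparison.

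**4. Illustration of sensitivity.** The documents give no value for a(j) − a(c), so the shifts below are assumptions. Let b be the false shift in SD units of the change score, with no true effect, n = 17 per arm (IV.C, IV.F) and two-sided 5% tests. The noncentrality is b / √(2/17) = 2.915 × b. The t-test has 32 df; the Tukey column is for one pair among three arms with 48 df.

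| b (assumed) | noncentrality | false positives, t-test | false positives, one Tukey pair |
|---|---|---|---|
| 0 | 0 | 5.0% | 1.9% |
| 0.1 | 0.29 | 5.9% | 2.4% |
| 0.25 | 0.73 | 10.9% | 5.3% |
| 0.5 | 1.46 | 29.3% | 17.9% |

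Section IV.F writes out the Tukey comparisons for lipids, insulin sensitivity and, in Aim 2, respiration. Applying them to PKC epsilon is my assumption.

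**The case against.** The best defence is that most of the measurement is instrumental. Lipids are ratios to internal standards, PP2A follows a manufacturer's kit, and cytochrome c is a measured test. Aim 3 respiration is normalised to vehicle, has a triolein control and is corrected for residual oxygen consumption. PKC may have its own activity assay. Much of this stands, and it narrows the point to blot-read PKC epsilon and respiration acceptance. It does not close it: a measured test without a cut-off still leaves pass or fail to the operator, and normalisation acts only on samples that have been kept.

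A reader might infer more than the documents support:
- **That all primary outcomes are equally exposed.** The text describes no manual step in quantifying the lipids. The hypotheses for the mitochondrial/ER fraction also run in opposite directions (sphingolipids down, DAG up), so a general handling error could not favour both.
- **That the results will be biased.** The documents do not say that laboratory staff will know the allocation.
- **That knowing the visit is as harmful as knowing the arm.** Step 3 shows that it largely cancels.
- **That Aim 1 correlations between lipids and signalling are distorted.** None is planned; Aim 1 correlates lipid change with change in insulin sensitivity.
- **That the assay order for scarce tissue adds discretion.** A fixed order limits it.
- **That the pilot fall in C18:0 ceramide gives a scale.** It is an internal-standard readout after a combined intervention that is not one of the randomised arms, so it says nothing about blots or sample acceptance.

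**Conclusion.** The gap is real and worth closing. Arm is not withheld from laboratory staff, and at least two kinds of primary outcome include a step where knowing it could matter. The conclusion rests on three readings: that the trial is open-label, which is inferred from the nature of the arms and not stated; that PKC epsilon is read from the blot, which the protocol should settle; and that the acceptance rule has no cut-off, since none is given.

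The size of any bias cannot be derived from the documents. The table shows only that, at 17 per arm, a false shift of 0.1 SD would do little and one of 0.5 SD would raise the error rate of a Tukey pair from 1.9% to 17.9%. Nothing places the trial at either end. This is an inexpensive safeguard that should be added, not evidence that the comparisons are invalid.

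**What to change.** **Muscle biopsy paragraph, IV.C.** Label stored aliquots with a study code that hides arm and visit. Run each participant's stored pre and post samples in the same batch or gel, with arms spread over batches. Lock assay values and all accept/reject decisions before the code is broken. Name who holds the key, since the protocol describes no such role.

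**Mitochondrial Respiration paragraph, IV.C.** Withhold arm from the respirometry operator. Visit cannot be hidden for fresh tissue. Set the cytochrome c acceptance cut-off in advance and report rejected samples by arm and visit.

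**Outcome Measure(s), IV.A.** State whether the PKC epsilon primary outcome is blot translocation or a separate activity assay, and reconcile this with the tissue list in IV.E.

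**Cost.** Label coding, batch planning and a key holder; no new visit, procedure or participant. The interventions are delivered by separate NORC cores, so keeping allocation from the laboratory looks practicable. The downside is that stored baseline samples wait for the second visit, through the three-month intervention and the two weeks of weight stability. Section III supports frozen tissue for fractionation; that blots and PP2A can also use stored tissue is an assumption to confirm.

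### The delayed-intervention control is said to rule out effects of health information and investigator contact, but as described it does not share the contact given within the two active arms

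*Combined protocol and SAP*

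**What the plan says.** Section IV.C of the protocol randomises participants to endurance exercise, diet-induced weight loss or delayed intervention for three months. Item 3 says of the last arm: "This group of individuals will serve as our free-living control group". It goes on to say that this arm will guarantee that no changes in the other two "are due to receipt of health information, exercise testing, or contact with investigators".

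The same section describes what the active arms receive between the two clamps.

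- **Exercise (item 1):** "Participants will perform supervised exercise 4x/week as well as exercise 1x/week on their own". On weight: "Participants will be weighed weekly, and will be instructed to consume more food to prevent weight loss during this intervention". On testing: "Maximal exercise testing will be performed half way through the intervention, and exercise prescriptions updated every 2 weeks".
- **Diet (item 2):** participants are weighed "weekly and will meet bi-weekly in group sessions to receive nutritional/behavioral counseling". After the three months, "subjects will transition to their normal diet for 2 weeks of weight maintenance, supervised by research dieticians".

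For the control, item 3 adds only that these participants may choose an intervention once they have finished the study.

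Section IV.F then compares the groups by one-way ANOVA with Tukey's procedure, and names control versus exercise and control versus diet as examples. Section IV.A lists change in insulin sensitivity as a primary outcome for Aims 1 and 2.

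**The concern.** The protocol names three alternative explanations for a change in an active arm (health information, exercise testing and investigator contact) and says the control excludes all of them. A control excludes an explanation only if it is exposed to it to the same degree. Here most of the contact and information is delivered inside the exercise and diet programmes, and nothing comparable is described for controls.

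What is at stake is the wording of the conclusion. A difference from control estimates the effect of the whole package: training or diet together with its supervision, counselling and weighing. If the sentence stands, a report could cite it as evidence that attention effects were excluded by design when they were not. Section I also plans to compare the two interventions to learn about mechanisms. Those arms differ from each other in amount and type of contact, so that comparison should be read in the same way.

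**Working it through.** The plan gives no figure for this point, so there is none to reproduce. The check sets the arms side by side and counts scheduled contacts as weeks × frequency.

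**Inputs.** Frequencies come from section IV.C, items 1 to 3. The baseline treadmill test comes from the section IV.C paragraph on strength and exercise testing, and the final battery from the closing paragraph on the interventions. Three months is taken as 12 to 13 weeks. This is an assumption; the pilot diet programme is described as lasting 12 weeks.

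| Element | Exercise | Diet | Control |
|---|---|---|---|
| Screening, baseline battery and clamp | yes | yes | yes |
| Final battery and clamp | yes | yes | yes |
| Supervised sessions | 4 × 12 = 48 to 4 × 13 = 52 | none described | none described |
| Weighings | 12 to 13, with food instruction | 12 to 13 | none described |
| Group counselling | none described | 12 / 2 = 6 (13 weeks also gives 6 whole sessions); if twice a week, 2 × 12 = 24 to 2 × 13 = 26 | none described |
| Dietician-supervised maintenance | none described | 2 weeks | none described |
| Maximal exercise tests (baseline + middle + final) | 1 + 1 + 1 = 3 | 1 + 0 + 1 = 2 | 1 + 0 + 1 = 2 |

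Weighings and supervised sessions may fall on the same visit, so the rows are not added together.

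**The three named factors in turn**

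1. *Exercise testing.* Diet versus control is 2 − 2 = 0, so this part of the statement holds for diet. Exercise versus control is 3 − 2 = 1 extra test.
2. *Health information.* The diet arm has group counselling. The exercise arm has instruction on food intake and a revised exercise prescription every two weeks. For controls nothing is described after entry, so this factor is unmatched in both contrasts.
3. *Investigator contact.* This is matched at screening, the test batteries and the clamps. It is unmatched in between: 48 to 52 supervised sessions for exercise, 12 to 13 weighings plus counselling for diet, and none described for control.

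**Shared food before the clamps.** Section IV.C says food is provided to all volunteers for 3 days before each clamp, whereas section IV.E says an approach of that kind was excluded. Neither passage distinguishes between arms, so the comparison above does not depend on which applies.

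**The case against.** The strongest defence is that the sentence in item 3 refers to information, testing and contact that come from taking part in the study, not from the interventions. On that reading the control does much of its job: all arms share screening, baseline and final testing, overnight stays and clamps. Supervision and counselling are also how training and diet are delivered, so a package effect is the natural contrast. Nothing in section IV.F tries to isolate exercise or diet net of contact. The aims are mechanistic, and the first planned analysis correlates lipid change with insulin-sensitivity change in the whole group.

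Much of this stands. The control is useful, and comparing packages is a legitimate design. But item 3 does not limit itself to study-related contact; it makes an absolute statement about all three factors. The defence supports a narrower sentence than the one written.

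Three stronger readings are tempting and are not supported.

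- A reader might infer that the control supports no part of the statement. It does support part: exercise testing is matched for diet, and assessment contact is matched for both active arms. Nor does either active arm carry every unmatched element. The group counselling is described only for diet and the mid-study test only for exercise.
- A reader might take it as established that controls have no contact between batteries. That is inferred from the term free-living and from silence. Section IV.C also has subjects wear an activity recorder throughout the study, so monitoring as such is not confined to the active arms.
- A reader might infer that the stable-weight condition before the final clamp cannot be checked in controls. The documents only leave the method undescribed. Having controls weigh themselves weekly would not match supervision or counselling and might change the behaviour of a free-living comparator.

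**Conclusion.** The statement in section IV.C, item 3, is wrong as written. For health information and for contact within the intervention period it claims a property that the described design lacks. For exercise testing it is right for diet versus control and off by one test for exercise versus control.

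This rests on four assumptions: three months is 12 to 13 weeks; the mid-study maximal test belongs only to the exercise arm, under which it is listed; the final battery, written for participants generally, includes controls; and the absence of any described interim contact for controls reflects what is intended.

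The documents give no size for an attention effect, so none is claimed. A reader might go further and infer that attention explains the expected improvements, or that the comparisons with control are invalid. Nothing in the documents shows either. The comparisons remain valid estimates of package effects. Sample size, power, alpha, endpoints and the planned tests are unaffected.

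**What to change.** Replace the sentence in section IV.C, item 3, with wording to this effect:

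> The delayed-intervention control accounts for the passage of time, repeated assessment and contact at the assessment visits. Differences between an active arm and control are effects of the whole intervention package, including its counselling, supervision and contact and, for exercise, one additional maximal test. Effects of attention are not excluded.

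Carry the same interpretation into section IV.F for the comparisons with control. If interim contact with controls is in fact intended, describe its content and frequency, and limit the claim to what is then matched.

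The cost is a few lines of text and a less favourable claim for the control. No visit, measurement, arm or analysis needs to be added.
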